8.2.2 Biospecimen Evaluations

Blood will be collected under this protocol by the following methods:

- Venipuncture will be performed with single-use needles. Venous blood samples will be used as follows:

- Safety evaluations described in section 8.3.
- Shipment to the research laboratory in Bamako and NIAID for evaluation (including assays described in section 8.2.3) and storage.
- Blood smear and dried blood spot for Pf RT-PCR if unable to obtain ample sample from finger prick.
- Finger prick will be performed using single-use disposable lancets. Finger prick blood samples will be used as follows:
 - Blood smear and dried blood spot for Pf RT-PCR.

The amount of blood drawn for research purposes will be within the limits allowed for adult research subjects by the NIH Clinical Center: no more than 10.5 mL/kg or 550 mL (whichever is smaller) over an 8-week period.

The collection schedule, volumes, and test tubes are presented in section 1.3.

8.2.3 Correlative Studies for Research/Pharmacokinetic Studies

The following evaluations will be performed according to the schedule presented in section 1.3.

Blood smear: Thick blood smears will be prepared and analyzed by the standard WHO method (section 2.2.3) to identify Pf infection for the primary endpoint. This evaluation will be performed centrally in the laboratory in Bamako, unless the subject is displaying signs or symptoms of clinical malaria, in which case the blood smear will be analyzed at the time of the scheduled or unscheduled visit.

Pf RT-PCR: RT-PCR will be performed to identify Pf infection as a secondary endpoint. This evaluation will be performed at the University of Washington on coded dried blood spots.

PK studies: Blood L9LS concentrations will be measured by Meso Scale Discovery LLC-based automation platform. The concentration at the visit prior to the first Pf infection will be used to assess L9LS-mediated protection. This evaluation will be performed at the NIAID.

ADA detection: Assays for detection of ADA will be performed at specified timepoints (section 1.3) following product administration and compared to baseline status. This evaluation will be performed at the NIAID.

Parasite genotyping: For subjects who become infected during the study, coded blood samples collected around the time of the first infection will be used to perform a genotypic sieve analysis to analyze sequences of breakthrough parasites (section 9.4.11). This evaluation will be performed by [name] at the Harvard School of Public Health.

8.2.4 Samples for Genetic/Genomic Analysis

8.2.4.1 Description of the scope of genetic/genomic analysis

Genetic testing performed in this protocol will be limited to analyzing the genetic material of infection-inducing parasites in blood samples. No human genetic analyses will be performed.

8.2.4.2 Description of how privacy and confidentiality of medical information/biological specimens will be maximized

Privacy and confidentiality of medical information and biological samples is described in section [10.3](#).

8.2.4.3 Management of Results

As no human genetic analyses will be performed in this protocol, no genetic results will be returned to subjects.

8.2.4.4 Genetic counseling

Not applicable.

8.3 SAFETY AND OTHER ASSESSMENTS

The following study procedures and evaluations will be done according to the schedule in section [1.3](#) to monitor safety and support the understanding of the study intervention's safety. The assessment and collection of safety events such as AEs are described in section [8.4.2](#).

Physical Examination: As described in section [8.2.1](#), physical examination will also be performed for assessment of safety.

Vital Signs: Vital signs (temperature, blood pressure, and heart rate) will be collected at visits, including before and after study agent infusion, as described in section [8.2.1](#).

Safety Blood Laboratory Evaluations: The following safety laboratory evaluations will be performed at a frequency presented in section [1.3](#):

- CBC with differential.
- ALT, Cr.

Pregnancy Testing: Women will have a serum pregnancy test at screening and urine tests at enrollment, day 0 (confirmed negative prior to administration of the study agent), and monthly through the final study visit.

Pregnancy Prevention Counseling: Female subjects will be counseled on the importance of not becoming pregnant during study participation and on acceptable methods of contraception.

8.4 SAFETY DEFINITIONS, MANAGEMENT, AND SPONSOR REPORTING

8.4.1 Definitions

Adverse Event: An AE is any untoward or unfavorable medical occurrence in a human subject, including any abnormal sign (e.g., abnormal physical exam or laboratory finding), symptom, or disease, temporally associated with the subject's participation in the research, whether or not considered related to the research.

Adverse Reaction: An AR means any AE caused (see “Causality” below) by a study agent. ARs are a subset of all suspected adverse reactions (SARs; defined below) where there is reason to conclude that the study agent caused the event.

Suspected Adverse Reaction: SAR means any AE for which there is a reasonable possibility that the study agent caused the AE.

Per US FDA guidance:

For the purposes of IND safety reporting, “reasonable possibility” means there is evidence to suggest a causal (see “Causality” below) relationship between the study agent and the AE. A SAR implies a lesser degree of certainty about causality than an AR, which means any AE caused by a study agent.

SARs are the subset of all AEs for which there is a reasonable possibility that the study agent caused (see “Causality” below) the event. Inherent in this definition, and in the requirement to report SARs, is the need for the sponsor to evaluate the available evidence and make a judgment about the likelihood that the study agent actually caused the AE.

The sponsor is responsible for making the causality judgment.

Serious Adverse Event: An SAE:

- is an AE that results in death.
- is an AE that is a life-threatening event (places the subject at immediate risk of death from the event as it occurred).
- is an AE that requires inpatient hospitalization or prolongs an existing hospitalization.

NOTE:

- Hospitalization is considered required if outpatient treatment would generally be considered inappropriate.
- Same-day surgical procedures that are required to address an AE are considered hospitalizations, even if they do not involve an overnight admission.
- Hospitalization due to a condition that has not worsened and that pre-dates study participation (e.g., elective correction of an unchanged baseline skin lesion), or due to social circumstance (e.g., prolonged stay to arrange aftercare), or that is planned/required “per protocol” AND that proceeds without prolongation or complication, is NOT considered an SAE by this criterion.
- is, or results in, a persistent or significant incapacity or substantial disruption of the ability to conduct normal life functions.
- is a congenital anomaly/birth defect/miscarriage/stillbirth.

NOTE: This definition is more inclusive than some commonly published definitions. It includes an affected conceptus/neonate whose:

- biological mother was exposed to a study agent at any point from conception through the end of the pregnancy, AND/OR, if breastfeeding, the 30-day neonatal period; or

- biological father was exposed to a study agent at any point during the 90 days prior to conception.

This is separate from, and in addition to, general reporting of pregnancy in a study participant or female partner of a male participant (see section [8.4.2.3.4](#) below).

- is a medically important event.

NOTE: Medical and scientific judgment should be exercised. Events that significantly jeopardize the subject and/or require intervention to prevent one of the SAE outcomes listed above are generally considered medically important, and are thus SAEs.

Unexpected Adverse Event: An AE is unexpected if it is not listed in the investigator's brochure or package insert (for marketed products) at the frequency, AND specificity, AND severity that has been observed.

NOTE:

- Such events should also be evaluated for possible reporting as unanticipated problems (UPs) (see section [8.4.2.3.3](#) below).
- Unexpected, as used in this definition, also refers to AEs or SARs that are mentioned in the investigator's brochure as occurring with a class of drugs/biologics, or as anticipated from the pharmacological properties of the study agent but are not specifically mentioned as occurring with the particular study agent under investigation.

Serious and Unexpected Suspected Adverse Reaction (SUSAR): A SUSAR is an SAR (defined above) that is both serious and unexpected.

Unanticipated Problem: A UP is any incident, experience, or outcome that meets all the following criteria:

1. Unexpected (in terms of nature, severity, or frequency) given
 - a. the research procedures that are described in the protocol-related documents, such as the EC-approved research protocol and informed consent document; and
 - b. the characteristics of the subject population being studied; and
2. Related or possibly related to participation in the research (possibly related means there is a reasonable possibility that the incident, experience, or outcome may have been caused by the procedures involved in the research), and
3. Suggests the research places subjects or others (which may include research staff, family members or other individuals not directly participating in the research) at a greater risk of harm (including physical, psychological, economic, or social harm) related to the research than was previously known or expected.

NOTE:

- Per the sponsor, an SAE always meets this "greater risk" criterion.
- An incident, experience, or outcome that meets the definition of a UP generally will warrant consideration of changes to the protocol or informed consent form, or to study procedures (e.g., the manual of procedures for the study), in order to protect the safety, welfare, or rights of participants or others. Some UPs may

warrant a corrective and preventive action plan at the discretion of the sponsor or other oversight entities.

Unanticipated Problem that is not an Adverse Event (UPnonAE): A UPnonAE belongs to a subset of UPs that:

- meets the definition of a UP, AND
- does NOT fit the definition of an AE or an SAE.

NOTE: Examples of UPnonAEs include, but are not limited to:

- a breach of confidentiality
- prolonged shedding of a vaccine virus beyond the anticipated timeline
- unexpectedly large number of pregnancies on a study
- subject departure from an isolation unit prior to meeting all discharge criteria
- accidental destruction of study records
- unaccounted-for study agent
- overdosage, underdosage, or other significant error in administration or use of study agent or intervention, even if there is no AE/SAE
- development of an actual or possible concern for study agent purity, sterility, potency, dosage, etc.

NOTE: A decision to temporarily quarantine, or to permanently not use all or part of study agent supply due to an unexpected finding or event (e.g., particulate, cloudiness, temperature excursion), even if there is no known or proven issue (i.e., out of an “abundance of caution”), is considered a UPnonAE.

Protocol Deviation: Any change, divergence, or departure from the EC-approved research protocol (except for some missed visits as specified in section 7.3).

1. **Major deviations:** Deviations from the EC-approved protocol that have, or may have the potential to, negatively impact the rights, welfare, or safety of the subject, or to substantially negatively impact the scientific integrity or validity of the study.
2. **Minor deviations:** Deviations that do not have the potential to negatively impact the rights, safety, or welfare of subjects or others, or the scientific integrity or validity of the study.

Noncompliance: Failure of investigator(s) to follow the applicable laws, regulations, or institutional policies governing the protection of human subjects in research, or the requirements or determinations of the EC, whether intentional or not.

1. **Serious noncompliance:** Noncompliance, whether intentional or not, that results in harm or otherwise materially compromises the rights, welfare and/or safety of the subject. Noncompliance that materially affects the scientific integrity or validity of the research may be considered serious non-compliance, even if it does not result in direct harm to research subjects.
2. **Continuing noncompliance:** A pattern of recurring noncompliance that either has resulted, or, if continued, may result in harm to subjects or otherwise materially

compromise the rights, welfare and/or safety of subjects, affect the scientific integrity of the study or validity of the results. The pattern may comprise repetition of the same non-compliant action(s), or different noncompliant events. Such non-compliance may be unintentional (e.g., due to lack of understanding, knowledge, or commitment), or intentional (e.g., due to deliberate choice to ignore or compromise the requirements of any applicable regulation, organizational policy, or determination of the EC).

8.4.2 Documenting, Assessing, Recording, and Reporting Events

ALL AEs, including those that may appear to have a non-study cause (see “Causality” below), will be documented (e.g., on the clinical chart/progress notes/clinical laboratory record), recorded (e.g., in the study-specified CRF/research database), and reported (e.g., cumulatively from the research database, or according to protocol-specified expedited reporting mechanism) to the sponsor from the time informed consent is obtained through the timeframe specified below. At each contact with the subject, information regarding AEs will be elicited by open-ended questioning and examinations.

AEs and SAEs will generally be recorded, assessed, and reported according to the timeframes outlined in [Table 2](#).

Table 2. Standard event recording, assessment, and reporting timeframes.

Event type	Record, assess, and report through
Related SAEs	End of subject participation in study, or if study personnel become aware thereafter
Unrelated SAEs	End of subject participation in study
Related non-serious AEs of grade 1 to 3	End of subject participation in study
All other related non-serious AEs	End of subject participation in study
Unrelated non-serious AEs	End of subject participation in study

8.4.2.1 Investigator Assessment of Adverse Events

The investigator will initially assess all AEs with respect to **seriousness** (according to SAE definition above), **severity** (intensity or grade, see below), and **causality** (relationship to study agent and relationship to participation in the research, see below). The Clinical Safety Office (CSO)/SMM is responsible for final/regulatory determinations of expectedness and causality.

8.4.2.1.1 Severity Grading

The investigator will grade the severity of fever (by non-oral temperature reading) and each blood laboratory testing AE according to the “Mali Adverse Event Grading Scale” provided in [APPENDIX B: MALI ADVERSE EVENT GRADING SCALE](#). Events that are not gradable

using this table (e.g., urinalysis abnormalities) will be graded according to the “Guidance for Industry: Toxicity Grading Scale for Healthy Adult and Adolescent Volunteers Enrolled in Preventive Vaccine Clinical Trials” which can be found at: <https://www.fda.gov/media/73679/download>.

Events that are NOT gradable using either of the above specified tables will be graded as follows:

- Mild = grade 1
- Moderate = grade 2
- Severe = grade 3
- Potentially life threatening = grade 4
- Death = grade 5

NOTE: A subject death should always be reported as grade 5.

8.4.2.1.1.1 Laboratory Value Assessment and Clinical Significance Criteria

Except as specified below, ALL abnormal lab values of grade 1 or above are REPORTABLE.

Grade 1 and 2 abnormal laboratory values are considered CLINICALLY SIGNIFICANT, and are to be recorded in the research database, and reported, if they meet ONE or more of the following criteria:

- result in a study agent dosage adjustment, interruption, or discontinuation
- are accompanied by clinically abnormal signs or symptoms that are likely related to the laboratory abnormality (e.g., clinical jaundice)
- indicate a possible organ toxicity (e.g., elevated serum creatinine)
- result in additional/repeat testing or medical intervention (procedures/treatments) (e.g., ECG to evaluate arrhythmia potential with a high serum potassium; one or more ECGs to assess an elevated troponin level; potassium supplementation for hypokalemia)
- indicates possible over-dosage
- are considered clinically significant by the investigator or SMM

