5.2 EXCLUSION CRITERIA

Individuals meeting any of the following criteria will be excluded from study participation:

1. Pregnancy, as determined by a positive urine or serum beta-human choriogonadotropin (β -hCG) test (if female).
2. Currently breastfeeding.
3. Behavioral, cognitive, or psychiatric disease that in the opinion of the investigator affects the ability of the subject to understand and comply with the study protocol.
4. Study comprehension examination score of $<80\%$ correct or per investigator discretion.

5. Hemoglobin, white blood cell, absolute neutrophil, or platelet count outside the local laboratory-defined limits of normal. (Subjects may be included at the investigator's discretion for "not clinically significant" values.)
6. Alanine transaminase (ALT) or creatinine (Cr) level above the local laboratory-defined upper limit of normal. (Subjects may be included at the investigator's discretion for "not clinically significant" values.)
7. Infected with human immunodeficiency virus (HIV), hepatitis C virus (HCV), or hepatitis B virus (HBV).
8. Known or documented sickle cell disease by history. (Note: Known sickle cell trait is NOT exclusionary.)
9. Clinically significant abnormal electrocardiogram (ECG; QTc >460 or other significant abnormal findings, including unexplained tachycardia or bradycardia).
10. Evidence of clinically significant neurologic, cardiac, pulmonary, hepatic, endocrine, rheumatologic, autoimmune, hematological, oncologic, or renal disease by history, physical examination, and/or laboratory studies including urinalysis.
11. Receipt of any investigational product within the past 30 days.
12. Participation or planned participation in an interventional trial with an investigational product until the last required protocol visit. [Note: Past, current, or planned participation in observational studies is NOT exclusionary; participation in the placebo arm of the Mali adult CIS43LS MAb trial (ClinicalTrials.gov Identifier: NCT04329104) is NOT exclusionary.]
13. Medical, occupational, or family problems as a result of alcohol or illicit drug use during the past 12 months.
14. History of a severe allergic reaction or anaphylaxis.
15. Severe asthma (defined as asthma that is unstable or required emergent care, urgent care, hospitalization, or intubation during the past 2 years, or that has required the use of oral or parenteral corticosteroids at any time during the past 2 years).

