9.4.5 Safety Analyses

Safety analysis will be primarily MITT where individuals who receive assignment but do not receive any product are excluded. Because of blinding and the brief length of time between assignment and administration, such cases will be very few.

Safety data will be presented by line listing and tables at the individual level to provide details on safety events such as severity, duration, and relationship to study product. The number and percentage of subjects with 1 or more AEs will be summarized by dose arm along with the exact 95% confidence intervals of the AE rate. For subjects experiencing more than 1 AE, the subjects will be counted once under the event of highest severity.

In the efficacy study, comparisons between the dose arms and the control arm will be additionally performed in terms of the proportions of solicited AEs, related AEs, and SAEs.

In the rare case of subjects receiving a regimen different from assignment, a per-protocol analysis will be performed as a secondary analysis, which will include subjects according to the product they actually receive in the study.

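### Grade 1–2 laboratory values reach the safety analysis only as AE records, under recording rules that conflict, so mild changes could be undercounted and new ones are not separated from pre-existing ones

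*Combined protocol and SAP*

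**What the plan says.** Section 8.4.2.1.1.1 opens with a broad default: "Except as specified below, ALL abnormal lab values of grade 1 or above are REPORTABLE". The exception follows: "Grade 1 and 2 abnormal laboratory values are considered CLINICALLY SIGNIFICANT, and are to be recorded in the research database, and reported, if they meet" any of six criteria. In paraphrase these are:

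- a change to study agent dosing;
- related signs or symptoms;
- possible organ toxicity;
- repeat testing or intervention;
- possible over-dosage;
- a judgement of significance by the investigator or the sponsor medical monitor (SMM).

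Section 8.4.1 defines an AE as "including any abnormal sign (e.g., abnormal physical exam or laboratory finding"), with no grade threshold. Section 8.4.2 requires all AEs to be documented, recorded and reported.

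The schedule in section 1.3 takes CBC with differential, ALT and creatinine at screening, at enrollment, on day 0 before dosing, and on days 7 and 14. Appendix B gives the grades.

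Section 9.4.5 plans individual-level listings and tables of safety events. It adds: "The number and percentage of subjects with 1 or more AEs will be summarized by dose arm", with exact confidence intervals. Arms are compared on solicited AEs, related AEs and SAEs. Section 9.4.1 promises descriptive statistics for endpoints of interest, and laboratory values are not a listed endpoint.

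Section 5.2 excludes people with haemoglobin, white cell, "absolute neutrophil, or platelet count outside the local laboratory-defined limits of normal", or with ALT or creatinine above normal. It lets the investigator include those whose values are judged not clinically significant.

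**The concern.** Safety and tolerability at 900 mg is a primary objective, and the trial is meant to prepare for studies in pregnant women. In healthy adults given one dose, small laboratory shifts are a plausible form for a signal to take.

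Such a shift must first become an AE record. Whether a grade 1–2 value does so depends partly on judgement and on whether someone repeated the test. A non-serious laboratory AE that is not a solicited symptom then enters the arm comparison only if it is also judged related.

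Neither the recording rule nor section 9.4.5 refers back to day 0. A long-standing grade 1 value that is re-tested meets a criterion. A new grade 1 value that is not re-tested, and meets no other criterion, does not. A report of no laboratory signal could then partly reflect recording practice.

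**Working it through.** **1. The recording rules side by side.**

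| Source | What it requires for an asymptomatic grade 1 value |
|---|---|
| 8.4.1 with 8.4.2 | It is an AE and is recorded |
| 8.4.2.1.1.1, default sentence | Reportable, unless the exception applies |
| 8.4.2.1.1.1, exception | Recorded and reported if it meets one of six criteria |

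The exception never says outright that other grade 1–2 values go unrecorded. If they are all recorded anyway, however, the exception does nothing. The natural reading is that some may be left out, which contradicts 8.4.1 and 8.4.2.

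**2. Which tests are exposed.**

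- Creatinine is the document's own example of organ toxicity: "indicate a possible organ toxicity (e.g., elevated serum creatinine").
- A raised ALT can reasonably enter by the same criterion.
- A mild asymptomatic fall in neutrophils, platelets or haemoglobin has no such obvious route. It depends mainly on repeat testing or a judgement of significance.
- The dosing-change criterion has little scope, because each person receives one dose and section 6.1.2.3 allows no modification.

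**3. What the analysis does with the values.** Section 9.4.5 contains no table of graded laboratory values, no shift table and no change from baseline.

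**4. The plan's own detection figure (section 9.2.1).** The inputs are n = 72 and a true rate of 0.032.

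Pr(at least 1) = 1 − (1 − 0.032)^72 = 0.904, matching the stated figure of over 90%. All entries of Table 3 also reproduce, from (1 − p)^n and the binomial tail. These figures assume that every event is recorded.

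**5. Sensitivity to incomplete recording.** Let c be the share of true grade 1–2 events that meet a criterion. It is **not in the documents**; 0.25 to 1 is an assumed range, taken as equal in both arms.

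Pr(at least 1 recorded) = 1 − (1 − 0.032c)^n

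| c | 0.032c | n = 72 | n = 216 |
|---|---|---|---|
| 1 | 0.032 | 0.904 | 0.999 |
| 0.75 | 0.024 | 0.826 | 0.995 |
| 0.50 | 0.016 | 0.687 | 0.969 |
| 0.25 | 0.008 | 0.439 | 0.824 |

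**6. Illustrative contrast between arms.** This uses the exact power of Fisher's test, 216 v 72, two-sided 0.05, by enumeration over both binomials with each rate multiplied by c. The rates are assumed, and the plan contains no such test of laboratory abnormalities.

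| True rate, L9LS v placebo | c = 1 | c = 0.5 | c = 0.25 |
|---|---|---|---|
| 20% v 5% | 0.915 | 0.496 | 0.165 |
| 15% v 3% | 0.862 | 0.407 | 0.067 |
| 15% v 5% | 0.626 | 0.235 | 0.047 |
| 10% v 3% | 0.415 | 0.138 | 0.006 |
| 10% v 5% | 0.186 | 0.069 | 0.007 |

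Losing events costs power in every row. In the smaller contrasts, power is low even when everything is recorded.

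**The case against.** The strongest reply is that the text supports full recording: the default sentence covers everything from grade 1 up, and the AE rules agree. That stands as far as it goes. It makes the problem a contradiction to resolve, not a demonstrated undercount.

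A reader might infer that a grade 1–2 value is recorded only when the investigator acts on it or calls it significant. The documents do not say this. Possible organ toxicity, possible over-dosage and related symptoms ("are accompanied by clinically abnormal signs or symptoms that are likely related to the laboratory abnormality (e.g., clinical jaundice")) each suffice, and the SMM can also make the call. Grade 2 values, such as ALT of 151 U/L or more, are also likely to prompt repeat testing.

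A reader might also infer bias between arms. Section 6.3.2 blinds those who conduct follow-up assessments, so the filter should act about equally in both arms.

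Nor are the values shown to be lost. Section 10.8.1 keeps study data in electronic CRFs, section 8.4.2.3 requires at least weekly review of accumulating data, and the DSMB may review study data. That makes the repair cheap, but it adds no laboratory analysis to section 9.4.5.

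Two limits apply to the baseline argument. A value outside local normal limits is not necessarily an Appendix B grade 1, and the local limits are not given. Appendix B also calls its values guidelines that depend on institutional parameters. Even so, its footnote on neutrophils expects lower values in this population, so pre-existing graded values are plausible.

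Finally, the primary safety endpoint covers 7 days, so the scheduled day-14 results bear on the wider safety objective and not on that endpoint.

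**Conclusion.** The point holds in a limited form. The recording rule for grade 1–2 laboratory values conflicts with the AE definition and the general recording rule, and section 9.4.5 specifies no analysis of the values themselves. Followed as written, the plan could undercount mild asymptomatic changes in both arms, chiefly in the CBC. It does not separate new abnormalities from pre-existing ones, although pre-dose day-0 results are collected.

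The expected consequence is understated rates and reduced ability to see a mild signal. The size cannot be determined from the documents. The figures above show sensitivity under assumed event rates and an assumed capture share common to both arms. It would be wrong to read them as the power this trial loses, since neither input is documented and no such test is planned. The change is worth making because it is specific and cheap and concerns a primary objective.

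**What to change.** 1. **Section 8.4.2.1.1.1, reconciled with 8.4.1 and 8.4.2.** State that the grade 1–2 criteria govern AE reporting only, and that all scheduled CBC, ALT and creatinine results are entered in the database. Align the AE definition and the general recording rule with this.
2. **Section 9.4.5.** Add text such as: *All scheduled day-7 and day-14 CBC, ALT and creatinine results will be graded by program from the laboratory value using Appendix B, whether or not recorded as an AE. The worst post-dose grade, and the shift from the pre-dose day-0 grade, will be tabulated by arm. In these tables an abnormality is treatment-emergent only if its grade is higher than on day 0.*

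The cost is one or two extra tables from samples already scheduled, with no new visit or blood draw.
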